11. APPENDICES	
Appendix I: Patient Data Collection Instruments/ Surveys	
Appendix II: HCCC Data Safety and Monitoring Plan	

1. Abstract

Sexual dysfunction is known to affect women newly diagnosed with cancer. This project will evaluate critical elements contributing to sexual dysfunction in women who have had surgery for gynecologic cancer and potentially provide a simple, easily applicable, and meaningful intervention. The subjects will complete a set of questionnaires about health, daily living, sexual activity, and pain before their surgery and three times following interventions. Each subject will be randomized to receive a perineal application of either lidocaine or a placebo to use immediately prior to any sexual encounters for approximately 6 months while maintaining a journal of sexual encounters and pain. The subjects and healthcare providers will be blinded to the treatment. Total participation will last approximately one year from the date of enrollment. We aim to better characterize elements related to sexual dysfunction in this specific population, and provide a treatment intervention to improve patient's quality of life, measured by changes in their physical, psychological or social functioning.

2. Background / Rationale

Sexual dysfunction in gynecologic cancer survivors has been well-documented [1]. Physical, psychological and social elements contribute to sexual dysfunction in this population. In 2011, over 88,000 women in the United States were diagnosed with gynecologic cancers. The majority of these cases affected women over the age of 60 [2]. Treatment of these cancers, while aimed at preventing death, may cause significant changes in physical, psychological or social functioning. These changes could lead to negative long-term effects on women's sexuality. It is important to recognize the multifactorial nature of this problem. While research exists regarding this topic, few studies include all three domains of sexual functioning. Even fewer studies are aimed at designing a specific intervention to address any aspect of the dysfunction [1]. One previous study from 1989 at the University of Iowa detailed the physical side effects of gynecologic cancer, showing that cancer survivors experienced decreased sexual activity, decreased sexual desire, decreased sexual excitement, less awareness of signs of orgasm, and dyspareunia compared to control groups [3]. In an additional study in the same year by the same group, the psychological effects of treatment are detailed. However, these outcomes were not directly related to feelings regarding sexual activity or the psychological effects of changes in sexuality and were not aimed at interventions [4]. In a study of breast cancer survivors, suffering from dyspareunia, Goetsch, et. al., described the use of 4% lidocaine jelly applied for 3 minutes to areas of pain on a cotton ball. This study found that this preparation reduced pain on exam and insertion when compared to saline placebo [5]. Lack of a full understanding of physical sexual dysfunction following a diagnosis and treatment of gynecologic cancer has been a detriment to developing interventions aimed at these issues.

3. Study Goals/Objectives

- The primary objective is to identify changes in sexual function assessments (Female Sexual Function Index survey, frequency of sexual encounters and a visual pain scale assessment with each encounter) after application of an aqueous lidocaine solution to the perineum versus a placebo application.
 - Hypothesis: Subjects surgically treated for ovarian, peritoneal, fallopian tube, cervical or endometrial cancer will have higher sexual functioning and less pain associated with sexual encounters after perineal treatment with aqueous lidocaine.
- Secondary objectives include characterizing the pre and post-treatment functioning of gynecologic cancer survivors with respect to physical, psychological, and social dimensions.
 - Subjects will complete nine short surveys (The Female Sexual Function Index, The PHQ-9, the GAD-7, the SPS, Rosenberg's Body Self-Esteem Index, the Severity of PTS Symptoms Scale, the Adverse Childhood Events Index, the SF-12, and the Dyadic Adjustment Scale) at their initial visit, assessing physical, psychological, and social elements related to sexuality. The same packet of surveys will be completed twelve weeks following surgery, after which, they will be randomized to a blinded perineal intervention. Survey packets will be completed 12 and 24 weeks following randomization to the perineal intervention.
 - A visual pain scale will be completed after each sexual encounter.
 - A diary documenting frequency of sexual encounters will be collected.

4. Study Population

Subjects comprising this study population include women undergoing initial consultation at the University of Iowa Hospitals and Clinics/Holden Comprehensive Cancer Center for a documented or suspected diagnosis of ovarian, fallopian tube, peritoneal, endometrial or cervical cancer. Each subject must be scheduled to undergo surgical treatment for their disease prior to enrollment. Enrollment will be offered and consent obtained by the Investigator or one of the sub-Investigators at the time of initial consultation in the outpatient clinic.

Subjects ultimately diagnosed with one of the previously mentioned gynecologic malignancies will remain eligible to continue on the trial, while those found to have no evidence of cancer will be excluded.

Inclusion/Exclusion Criteria:

4.1 Inclusion criteria

- Female
- Age 18-99

- Planned to undergo primary surgical treatment at the University of Iowa Hospitals and Clinics for a suspected or proven diagnosis of ovarian, fallopian tube, peritoneal, endometrial, or cervical cancer
- Able to give informed consent and follow study procedures
- No previous reactions to lidocaine applications
- GOG Performance Status of 0 or 1
- Reports having engaged in vaginal intercourse at least once in the last 12 months

4.2 Exclusion criteria:

- Failure to confirm invasive ovarian, fallopian tube, peritoneal, endometrial or cervical cancer by pathology from primary biopsy or surgery (subjects will not be eligible to continue the trial beyond the initial completion of the questionnaires)
- Diagnosis of another malignancy within the past five years, excluding basal cell carcinoma of the skin
- Patients undergoing primary or adjuvant external pelvic radiation (excluding adjuvant vaginal brachytherapy)
- Previous reactions to lidocaine applications
- Sexual partners' previous reactions to lidocaine applications

5. Study Design and Methods

5.1 Data Acquisition

Study data will primarily be obtained through questionnaires and self-reported data from a visual pain scale and a diary documenting frequency of sexual encounters.

5.1.1: The questionnaire packet consists of nine short surveys that capture information on psychological, social and physical elements previously cited as potential influences on sexual dysfunction. This survey packet will be completed prior to a surgical intervention with the intent to capture a “baseline” for the subject. Completion of the survey packet will be requested at the three month postoperative check-up visit and then at two more sequential three month follow-up visits. The perineal intervention will be introduced at the first three month postoperative visit.

5.1.2: Subjects will self-report potential discomfort related to each sexual encounter on a visual pain scale. These scales will be collected at each three month follow-up visit.

5.1.3: Subjects will be asked to maintain a diary/calendar documenting the frequency of sexual encounters and the successful or unsuccessful ability to

apply the perineal intervention. The diary/calendar will be collected at each three month visit.

5.2 Procedures

5.2.1: Primary surgical intervention

Subjects will be eligible and plan to undergo a primary surgical procedure for the treatment of their gynecologic cancer (ovarian, fallopian tube, peritoneal, endometrial or cervical) under one of the UIHC gynecologic oncologists. Surgical treatment of these cancers, which includes removing some or all of the gynecologic organs, may cause physical as well as perceived changes in sexual function. Surgical treatment for ovarian, fallopian tube, peritoneal, endometrial, and early stage cervical cancers is often the first option of treatment for appropriately selected patients and critical to a comprehensive treatment approach. It is the goal to systematically evaluate the changes in sexual function prior to and following primary surgery for these subjects.

5.2.2 Randomization

Patients will be randomized to receive either the lidocaine solution or a placebo using permuted block technique based on cancer origin. Patients and investigators are blinded to assignment. Only the Investigational Drug Service will maintain the blinded codes. Patient and investigator will be unblinded at the conclusion of the study. Patients are randomized 1:1 to each arm.

Randomization will be stratified by pathological category of cancer type.

Thirty subjects will be randomized within each of three groups:

1. Ovarian, fallopian tube, primary peritoneal cancer
2. Endometrial cancer
3. Cervical cancer

5.2.3 Evaluation of sexual dysfunction

The survey packet evaluates physical, psychological, and social elements related to sexuality. Each packet will be assembled into a large envelope and handed to the subject by the healthcare provider in the UIHC Gynecologic Oncology outpatient clinic. The surveys will be completed by the subject in the clinic (in a private area) on the day of the visit and then collected by the research data managers.

Each survey packet will contain:

1. Female Sexual Function Index: A self-report measure of sexual functioning
2. Patient Health Questionnaire 9 (PHQ-9): Instrument for screening, diagnosing, monitoring, and measuring the severity of depression.

3. Generalized Anxiety Disorder 7-item scale (GAD-7): A brief measure for assessing generalized anxiety disorder.
4. Social Provisions Scale (SPS): Instrument to assess provisions of social relationships.
5. Rosenberg's Body Self-Esteem Index: Scale that measures global self-worth by measuring both positive and negative feelings about the self.
6. Severity of Posttraumatic Stress Symptoms-Adult: Assesses the severity of posttraumatic stress disorder following a particular event or experience.
7. Adverse Childhood Events Index: A scale measuring types of physical, verbal, and emotional childhood trauma
8. SF-12: A generic measure of health status
9. Dyadic Adjustment Scale: A relationship adjustment self-report measure.

5.2.4 Diary of Sexual Encounters

A diary of sexual encounters during the 24 weeks of observation will be kept by participating subjects. On the calendar, subjects will be asked to document date of sexual encounter and an accompanying successful or unsuccessful perineal application of the intervention. For each encounter, subjects will also be asked to mark a visual pain scale.

5.2.5 Adverse Events

Study participants will be asked if there have been any reactions to the solution supplied for perineal application at each clinic visit. They will be encouraged to contact their primary gynecologic oncologist or the study chair immediately should any adverse reactions be experienced with the perineal application.

Each questionnaire packet will be reviewed immediately following collection for an immediate assessment to positive responses to the depression and suicidal ideation items of the PHQ-9. If the PHQ-9 score reflects severe depression, the clinician overseeing the patient's care for their gynecologic malignancy will be notified and asked to use their clinical discretion for intervention and appropriate referrals within the UIHC health system.

6. Study Procedures

6.1 Self-reported measures of physical, psychological and social stressors influencing sexual function

Patient-completed surveys, measuring the different elements of sexual dysfunction, will be completed at their initial visit, following their assessment by a UIHC

gynecologic oncologist, and their decision to pursue a surgical intervention for their gynecologic cancer. At the twelve week postoperative visit, and if a pathologic diagnosis of cancer is confirmed, subjects will be asked to complete the same survey packet. At subsequent 3 and 6 month follow-up visits, subjects will be asked to complete the survey packet following the visit with their gynecologic oncology healthcare provider.

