6.2 Aqueous Lidocaine and Placebo Perineal Application

Once subjects have a confirmed diagnosis of their gynecologic cancer, and they complete the survey packet at their 12-week follow-up visit, they will be randomized to receive a solution containing either aqueous lidocaine or a placebo. They will also be given a package of cotton balls with instructions to put the solution on three cotton balls and apply them to the perineum/vaginal introitus for one minute prior to sexual intercourse. Subjects will be asked to document in their diary successful or unsuccessful application of the perineal solution. They will also be asked to complete a visual pain scale for each sexual encounter. Subjects will be reminded to bring the calendars to the return visit with a phone call.

The aqueous lidocaine/placebo solution will be supplied by the Investigational Drug Service. It will be labeled in a manner that does not identify the presence of active ingredient.

CALENDAR/SCHEDULE OF EVENTS

Procedures	Visit 1 Pre-surgery	Visit 2 (12 weeks post- surgery)	Visit 3 (24 weeks post-surgery)	Visit 4 (32 weeks post-surgery)
Informed Consent	x			
Inclusion / Exclusion Criteria	x			
Performance Status	x	x	x	x
Physical Exam	x	x	x	x
Questionnaires	x	x	x	x
Diary of Sexual encounters and lidocaine/placebo usage		x	x	x
Randomization		x		

7. Safety

7.1 Possible Adverse events of lidocaine include:

- Rare allergic reactions: Itching; hives; edema of the face or hands; tingling in the mouth or throat or chest tightness (which can cause trouble breathing).
- Other uncommon reactions: Blurred or double vision; confusion; dizziness; lightheadedness; or drowsiness; chest pain or an uneven heartbeat; skin rash; swelling in the area where this medicine is applied; and trembling (shaking).

7.2 Other risks of the study procedures include:

- Embarrassment: discomfort answering some of the questions of the surveys (subjects may skip any questions they choose).

7.3 Stopping Rules:

- Subject may stop participating at any time
- Subject not following instructions
- Gel becomes unavailable
- Attending physician decision to withdraw subject
- Breach of confidentiality

8. Statistical Evaluation/Considerations

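### Both adverse-reaction routes in 5.2.5 need the participant to blame the solution first, so the systemic symptoms listed in 7.1 may be under-reported in both arms, and no tabulation by arm is described

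*Combined protocol and SAP*

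**What the plan says.** Section 5.2.5 gives two routes by which a reaction can reach the study team. The first is scheduled: "Study participants will be asked if there have been any reactions to the solution supplied for perineal application at each clinic visit". The second is open between visits: participants are encouraged to "contact their primary gynecologic oncologist or the study chair immediately should any adverse reactions be experienced with the perineal application". The same section provides for one other safety review, of mood: "Each questionnaire packet will be reviewed immediately following collection for an immediate assessment to positive responses to the depression and suicidal ideation items". The Schedule of Events lists a physical exam at all four visits but has no adverse event row.

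Section 7.1 lists the possible events in two groups. The allergic group begins "Rare allergic reactions: Itching; hives; edema of the face or hands; tingling in the mouth or throat or chest tightness". The second group includes "Blurred or double vision; confusion; dizziness; lightheadedness; or drowsiness; chest pain or an uneven heartbeat; skin rash", followed by local swelling and trembling.

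On the diary, 5.2.4 says that "subjects will be asked to document date of sexual encounter and an accompanying successful or unsuccessful perineal application of the intervention", with a pain scale for each encounter. Sections 5.1.2, 5.1.3 and 6.2 describe the same content. Partners enter through one exclusion criterion in 4.2: "Sexual partners' previous reactions to lidocaine applications".

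Section 8 covers the FSFI, the sample size and mixed models for the questionnaire domains. It says nothing about summarizing adverse events.

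**The concern.** Both routes ask about an effect of the solution, not about symptoms. Before anything is recorded, the participant must judge that what she felt came from the product. For rash or swelling at the application site that judgment is easy. For dizziness, drowsiness, confusion or blurred vision it is not: she is blinded and recovering from cancer surgery, and other explanations are at hand.

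A randomized placebo arm makes this judgment unnecessary. If symptoms are collected regardless of cause, the two arms can be set side by side and the background rate shows itself in the placebo arm. Collection filtered by attribution gives up much of that advantage and lowers the counts in both arms. What is at stake is how much reassurance a low or zero count from this pilot can give about the systemic events that the protocol itself lists.

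**Working it through.** **The text, side by side**

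| Element | What is described | Captures a symptom the participant does not link to the solution? |
|---|---|---|
| Visit question (5.2.5) | Reactions to the solution | No |
| Immediate contact (5.2.5) | Adverse reactions to the application | No |
| PHQ-9 review (5.2.5) | Depression and suicidal ideation | Only those |
| Physical exam (Schedule of Events) | Every visit | Unlikely for a transient symptom that has passed |
| Diary (5.1.2, 5.1.3, 5.2.4, 6.2) | Date, application success, pain scale | No symptom field described |
| Partner reaction | Exclusion criterion in 4.2 only | Not asked |
| Analysis (Section 8) | FSFI and questionnaire models | No adverse event table described |

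**The plan's own figure.** The documents give no safety figure to reproduce. The one calculation in Section 8 is for efficacy: 15 per group, difference 9.3, SD 10.0, one-sided 0.05, two-sample t-test. It gives 79.9% against the stated 80%. The present point does not depend on it.

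**Size of the arm.** Section 5.2.2 randomizes 30 women in each of three cancer groups, 1:1. That is 3 × 30 = 90, or 90 / 2 = 45 per arm. The figure assumes that all 90 are randomized and that each woman uses the solution at least once.

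**What a zero count would mean.** With no event in n = 45, the one-sided 95% upper bound on the recorded rate is 1 − 0.05^(1/45) = 6.44%. If a fraction c of true events is recorded, the recorded rate is c × p, so the bound on the true rate p is 6.44% / c:

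- c = 1: 6.4%
- c = 0.75 (assumed): 6.44 / 0.75 = 8.6%
- c = 0.50 (assumed): 6.44 / 0.50 = 12.9%

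**Chance of seeing at least one event in 45**, 1 − (1 − c × p)^45, with assumed true rates:

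| True rate p | c = 1 | c = 0.50 |
|---|---|---|
| 1% | 36% | 20% |
| 2% | 60% | 36% |
| 5% | 90% | 68% |
| 10% | 99% | 90% |

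**Between-arm comparison.** For assumed rates of 5% and 15% with 45 per arm, two-sided power at 0.05 is about 35% with full capture. With half capture the recorded rates are 2.5% and 7.5%, and power is about 19%. Both use the normal approximation, which is rough at such counts.

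**Interval between questions.** Section 3 places the later packets 12 and 24 weeks after randomization. The Schedule of Events places Visits 2, 3 and 4 at 12, 24 and 32 weeks after surgery. From Visit 2 to Visit 3 is 24 − 12 = 12 weeks in both. Visit 4 falls 24 weeks after randomization in Section 3 but 32 − 12 = 20 weeks after Visit 2 in the schedule, which makes the last interval 12 or 8 weeks.

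**The case against.** The strongest reply is that the plan does not wait for visits. A reader of the visit question alone might infer that reactions are gathered only by recall at visits 12 weeks apart. The next sentence of 5.2.5 contradicts that: participants are encouraged to call at once, and this suits acute events such as chest pain or facial swelling. A physical exam takes place at every visit, and the last interval may be 8 weeks rather than 12. All of this stands. What it does not remove is the attribution step, because the call is also for reactions to the application.

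Second, under blinding the loss should be broadly similar in the two arms, so it mainly costs counts and precision. That also stands, unless an effect such as numbness reveals the assignment, in which case reporting could differ by arm. Third, power to compare safety between arms is low even with full capture. That is true, but it makes the observed counts and their bounds the main safety information that a pilot can offer, and those depend directly on capture.

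Fourth, the attribution argument fits the systemic symptoms, not local rash or swelling. Accepted.

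Fifth, the contents list Appendix I (data collection instruments) and Appendix II (the data safety and monitoring plan), and neither text is available here. The diary form may carry a symptom field, and reporting rules may sit in Appendix II. So the claim is limited to what the body of the protocol describes. The body does, however, state the question put to participants.

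**Conclusion.** The point holds as a matter of likely under-reporting. On both routes in 5.2.5 the participant's own attribution comes first, so the systemic symptoms in 7.1 may be under-recorded in both arms. The body of the protocol describes no symptom field in the diary, no partner question and no tabulation by arm. The size cannot be fixed from the documents, because they give no event or capture rates. Under assumed capture of 75% to 50%, a zero count in 45 women is compatible with true rates up to 8.6% to 12.9%, instead of 6.4%.

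Three stronger readings are not supported. The documents do not show that events would be missed, only that they may be. They do not name a partner risk: Section 7 lists none, and 4.2 only implies that a partner's reaction is relevant. And no planned safety comparison is being weakened, since Section 8 plans none and states feasibility and estimates of relative efficacy as the pilot's aims, with no claim of acceptability. The design permits a comparison that the plan does not take up.

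**What to change.** - In 5.2.5, replace the question about reactions at the visits after randomization with a short checklist of the 7.1 symptoms, asked regardless of believed cause. Keep the immediate-contact route.
- Add a yes/no symptom line to each diary entry. The checklist still relies on recall between visits; this line is what shortens it. The participant may also note a partner reaction there, if the ethics board agrees that partner information can be collected in this way, since Section 4 describes consent for subjects only.
- Add an adverse event row to the Schedule of Events. In Section 8, state that counts will be tabulated by arm with confidence bounds.
- Check Appendices I and II, and cross-refer to them if they already contain any of this.
- Reconcile the timing of Visit 4 between Section 3 and the Schedule of Events, so that the period covered by the last checklist is defined.

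The cost is a short form, one diary line, one schedule row and one table, plus the ethics question on partner information. More unrelated symptoms will be recorded in both arms, and formal between-arm power stays low.

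### Packets are screened for positive suicidal-ideation answers, but the only written trigger for notifying the treating clinician is a PHQ-9 score reflecting severe depression

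*Combined protocol and SAP*

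**What the plan says.** Two consecutive sentences in Section 5.2.5 (Adverse Events) govern this step.

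- The check takes place as soon as a packet is handed in, and its stated purpose is "an immediate assessment to positive responses to the depression and suicidal ideation items of the PHQ-9".
- The action: "If the PHQ-9 score reflects severe depression, the clinician overseeing" the woman's cancer care is to be told, and is asked to use judgement about intervention and referral. No numeric cut-off for severe depression is given.

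Three other places bear on it.

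- Section 5.2.3: packets are filled in privately in clinic "on the day of the visit and then collected by the research data managers".
- Section 6.1: the first packet "will be completed at their initial visit, following their assessment by a UIHC" gynecologic oncologist. At the two follow-up visits after randomisation, women "complete the survey packet following the visit with their gynecologic oncology healthcare provider".
- Section 7.2, on the discomfort of answering the surveys: "subjects may skip any questions they choose".

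**The concern.** The check and the action do not match. The check works on individual items and names suicidal ideation. The action depends on a score and names only severe depression. Staff who follow the text exactly could find a positive ideation answer, see that the score is not severe, and notify no one while fully complying with the protocol.

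What is at stake is the safety of an individual participant, from the pre-surgery packet onward. No estimate or test in the trial is affected.

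**Working it through.** No arithmetic is needed for the main point; it rests on comparing what is screened with what triggers action.

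**Step 1. Apply the written rule to each possible result.**

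| Ideation item | PHQ-9 score | Looked for by the check? | Written condition for notification met? |
|---|---|---|---|
| Positive | Severe | Yes | Yes |
| Positive | Not severe | Yes | No |
| Positive | Incomplete | Yes | Not determined: no rule for skipped items |
| Not positive | Severe | Yes, through the depression items | Yes |

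The second and third rows are the gap. The second assumes that a positive ideation answer can occur with a non-severe score. The documents give neither PHQ-9 item scoring nor a severity cut-off, so this cannot be confirmed from them. The third follows from Section 7.2, which allows skipping, together with the absence of any scoring rule for incomplete forms.

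**Step 2. Look for another trigger in the supplied text.**

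- The other contact route in Section 5.2.5 is for women reporting reactions to the applied solution.
- Section 7.2 lists embarrassment as the survey risk and describes no suicidality pathway.
- The stopping rules in Section 7.3 do not mention suicidality.
- Elsewhere (Sections 3 and 5.2.3) the PHQ-9 appears only as one of the nine surveys.

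No second trigger was found.

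**Step 3. Ask whether the clinician would learn of the answer anyway.** The order of packet and clinician contact, from Section 6.1 and the schedule of events, is:

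- Visit 1: packet after the oncologist's assessment.
- Visit 2: order not stated.
- Visit 3: packet after the provider visit.
- Visit 4: packet after the provider visit.

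Packets after clinician contact: 1 + 0 + 1 + 1 = 3 of 4, or 4 of 4 if Visit 2 follows the same order. For these packets the consultation has already taken place when the ideation item is answered. This count describes visit order; it does not measure how often the gap would occur.

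**The case against.** The strongest reply is that the first sentence may already require action. An immediate assessment of positive ideation answers can be read as a clinical response, with the severe-score sentence adding one further escalation. Singling out ideation items would make little sense for a purely clerical check. That reading is possible, and it suggests the intent is sound. It still leaves unsaid who assesses, what follows, and whether the treating clinician is told, while the one condition that is spelled out omits ideation.

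Second, the bodies of Appendix I (instruments) and Appendix II (data safety and monitoring plan) were not supplied, and consent pages were removed before review. A scoring rule or suicidality procedure could be in any of them. This stands, and it limits the point to the text that could be read.

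Third, data managers collect the packets, but the protocol does not say who reviews them. If the reviewer were the treating clinician, the gap would close in practice. This also stands, although the notification sentence would have little purpose if the reviewer and the treating clinician were always the same person.

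Finally, no frequency is available and the statistical design is untouched. Both are true. Neither removes the mismatch.

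**Conclusion.** The concern holds. In the supplied text, suicidal ideation is screened for, but a positive answer is not itself a written reason to notify the treating clinician. This is a point that should be corrected, held with medium confidence because of the unseen appendices.

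The number of women affected cannot be estimated. The conclusion rests on two conditions: that positive ideation can accompany a non-severe or incomplete score, and that no unseen document already supplies the trigger.

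**What to change.** Replace the notification sentence in Section 5.2.5 with wording such as:

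> The treating clinician will be notified on the same day, where possible before the participant leaves clinic, if the PHQ-9 score reflects severe depression or if any suicidal-ideation item is answered positively, regardless of the score and even if other items were skipped.

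The clinical response stays at the clinician's discretion, as now. If Appendix II already contains such a trigger, cite it in Section 5.2.5 instead. This wording does not settle what to do when the ideation item itself is left blank, or when skipped items hold a score below severe with no positive ideation answer; the team may wish to add a line on each.

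The cost is small. The packet review already takes place, and packets are completed in clinic on the visit day, so same-day notice is practical. Because the protocol does not name the reviewer, the site should confirm who makes the notification. There will be some additional notifications, and some may need no action. Randomisation, blinding, power and analysis are unchanged.
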